#### **4.5 Duration of Follow Up**

Once treatment has been discontinued, patients will be followed with phone calls every 3 months until death or for 5 years, whichever occurs first. We will collect data on development of additional cancers, subsequent therapy (chemotherapy, radiation or surgery) for their cancer, and survival. Medical records including laboratory, pathology, operative, and radiology reports will be obtained at the discretion of the principal investigator with permission from the

patient. Patients removed from study for unacceptable adverse events will be followed until resolution or stabilization of the adverse event.

#### **4.6 Criteria for Removal from Study Treatment**

A patient will be withdrawn from the study treatment if any of the following events occur while on therapy:

- Interruption of scheduled therapy for greater than 6 weeks except as noted above in section 4.4.
- Intolerable adverse effects, laboratory abnormality or intercurrent illness that is judged by the investigator to be either physically or psychologically detrimental to the patient.
- Pregnancy.
- Patient non-compliance.
- Unresolved or recurrent Grade 3 or 4 toxicities except as noted above in section 4.4.
- Treatment with other anti-cancer drugs.
- Confirmed disease progression on therapy as outlined in Section 4.4 and Section 4.4.1.
- Withdrawal of informed consent (subject's decision to withdraw for any reason).
- Loss of ability to freely provide consent through imprisonment or involuntary incarceration for treatment of either a psychiatric or physical (e.g., infectious disease) illness.
- All subjects who discontinue study treatment should comply with protocol specified follow-up and survival procedures as outlined in Section 4.5. The ONLY exception to this requirement is when a **subject withdraws consent** for all study procedures **or loses the ability to consent freely** (i.e., is imprisoned or involuntarily incarcerated for the treatment of either a psychiatric or physical illness); in this case they will be deemed off study and no further follow up will be performed.

### **5. DOSING DELAYS/DOSE MODIFICATIONS**

Dosing delays and dose modifications on this study will be made at the discretion of the treating physician. No dose modifications will be allowed for nivolumab. Adverse symptoms prompting dose delay of greater than 6 weeks in any phase of the study will result in study discontinuation except as noted in section 4.4.

#### **5.1 Dose Modifications/Treatment Delays for Azacitidine and Entinostat Only**

In order to maintain dose –intensity and cumulative dose-delivery on this study, reasonable efforts will be made to minimize dose reduction and treatment delays as specified below. In case of toxicity, appropriate medical treatment should be used (including anti-emetics for nausea/vomiting, etc.) No dose escalation is planned for this study. For any event which is apparent at baseline, the dose modifications will apply according to the corresponding shift in toxicity grade, if the investigator feels it is appropriate. (e.g. if a patient has a grade 1 asthenia at baseline which increases to grade 2 during treatment, this will be considered as a shift of 1 grade and treated as a grade 1 toxicity for dose modification purposes). Where several toxicities with different grades or severity occur at the same time, the dose modifications applied should be the greatest reduction applicable.

Treatment will be modified based on treatment-related toxicity as described below for all patients receiving azacitidine and entinostat on Arm D, Arm E and Arm F. Dose omits due

to toxicity will not be made-up; patients may resume treatment once toxicity resolves as per the regular schedule.

5.1.1 White blood cell decreased/Neutrophil count decreased.

- See Table for dose adjustment criteria.
- Filgrastim or pegfilgrastim should not be given during nivolumab treatment.

5.1.2 Platelet Count Decreased.

- See table for the dose adjustment criteria.

5.1.3 Anemia

- There are no specific recommendations regarding management of anemia.
- Blood transfusions or erythropoietin stimulating agents may be used to treat chemotherapy-induced anemia at the discretion of the treating physician per current ASCO Guidelines. These state that “for patients with chemotherapy-associated anemia, initiating an erythropoiesis-stimulating agent (ESA) as hemoglobin (Hb) approaches, or falls below, 10 g/dL, to increase Hb and decrease transfusions”.

5.1.4 Diarrhea

If diarrhea develops, patient must be evaluated for potential signs or symptoms of infectious causes or nivolumab-related colitis. If these etiologies are excluded, patients will be instructed to begin taking loperamide at the earliest signs of:

- A loose stool.
- Occurrence of 1 to 2 more bowel movements than usual in one day, or Unusually high volume of stool,
- Loperamide should be taken in the following manner: 4 mg at the first onset of diarrhea, then 2 mg every two hours (4mg every 4 hours while asleep) around the clock until diarrhea-free for at least 12 hours. Additional antidiarrheal measures may be used at the discretion of the treating physician.
- If the measures above fail, the dose may be reduced as listed below.

5.1.5 Nausea/Vomiting

- Both entinostat and azacitidine use can lead to nausea and vomiting.
- Prophylactic 5-HT3 antagonist will be used on days when either entinostat or azacitidine will be administered. If nausea and vomiting persists despite these measures, more aggressive use of 5-HT3 antagonists or other anti-emetics can be used at the discretion of the treating physician.
- See table below for the dose adjustment criteria.

5.1.6 Metabolic/electrolyte abnormalities

- Entinostat is associated with multiple electrolyte abnormalities including hypermagnesemia, hyperglycemia, hypophosphatemia, hyponatremia, and hypocalcemia. Low values will be repeated as appropriate per institutional standard. Hyperglycemia will be corrected at the discretion of the treating physician.
- See table for the dose adjustment criteria.

5.1.7 Other non-hematologic toxicities

- Dose adjustments will not be made for alopecia, fatigue, or loss of appetite of any grade.
- For other grade 3 and 4 non-hematologic toxicities not described above, see Table for dose adjustment criteria.

| CTCAE System Organ Class (SOC) | Adverse Event   | Grade        | Azacitidine Dose Change  | Entinostat Dose Change                         |
|--------------------------------|---|--------------|--|--|
| Investigations                 | Neutrophil Count decreased                                  | Grade 1 or 2 | No Change  | No Change                                      |
|                                |   | Grade 3 or 4 | Omit for 2 weeks and reduce next cycle by 10 mg/m  | Omit for 2 weeks and reduce next cycle to 3 mg |
|                                | Platelet count decreased                                    | Grade 1 or 2 | No change  | No change                                      |
|                                |   | Grade 3 or 4 | Omit for 2 weeks and reduce next cycle by 10 mg/m  | Omit for 2 weeks and reduce next cycle to 3 mg |
|                                | White blood cell decreased                                  | Grade 1 or 2 | No change  | No change                                      |
|                                |   | Grade 3 or 4 | Omit for 2 weeks and reduce next cycle by 10 mg/m  | Omit for 2 weeks and reduce next cycle to 3 mg |
| Gastrointestinal disorders     | Diarrhea (Reduce dose only after optimal use of loperamide) | Grade 1 or 2 | No change  | No change                                      |
|                                |   | Grade 3 or 4 | Omit for 2 Weeks and reduce next cycle by 10 mg/m  | Omit for 2 weeks and reduce next cycle to 3 mg |
|                                | Nausea / Vomiting (reduce dose only after optimal use of    | Grade 1 or 2 | No change  | No change                                      |

|   |   |              |   |   |  |
|---|---|--------------|---|---|--|
|   | anti-emetics)   | Grade 3 or 4 | Omit for 2 weeks and reduce next cycle by 10 mg/m                             | Omit for 2 weeks And reduce next cycle to 3 mg  |  |
| Metabolism nutrition disorders                                       | -Hyperglycemia
-Hypoglycemia
- Hypophosphatemia
-Hyponatremia
-Hypocalcemia
-Hypercalcemia | Grade 1 or 2 | No change   | No Change   |  |
|   |   | Grade 3      | No change   | Omit for 2 weeks and reduce next Cycle to 3 mg if refractory to appropriate treatment |  |
|   |   | Grade 4      | No Change   | Omit for 2 weeks and reduce next cycle to 3 mg  |  |
| Other non-hematologic adverse events not mentioned above |   | Grade 1 or 2 | No change   | No change   |  |
|   |   | Grade 3 or 4 | Omit treatment until toxicity Resolves to Grade 1 then Dose reduce by 10mg/m  | Omit treatment Until toxicity Resolves to Grade 1 then dose reduce to 3 mg            |  |

If adverse events are noted on day 1 of any cycle of therapy then both agents should be held until treatment is deemed safe to administer. Unless otherwise specified, grade 3 or 4 toxicity should improve to grade 2 or better prior to resuming treatment.

If treatment is omitted for non-hematologic adverse events not described above both drugs should be dose-reduced unless the toxicity can be clearly attributed to entinostat or azacitidine specifically.

### 5.1.8 Hypersensitivity Reactions

Hypersensitivity reactions to azacitidine or entinostat should be managed as per standard of care at the treating institution. Severe reactions, such as hypotension requiring treatment, dyspnea requiring bronchodilators, angioedema or generalized urticaria require immediate discontinuation of study drug administration and aggressive symptomatic therapy. Subjects who experience a severe hypersensitivity reaction to treatment should not be re-challenged.

### 5.1.9 Special Considerations

Up to 2 dose reductions are allowed for azacitidine and one dose reduction for entinostat. For any grade 4 toxicity that recurs despite prophylaxis or dose reduction, study treatment should be discontinued.

## 5.2 Nivolumab dose delay criteria

Nivolumab administration should be only delayed for the following immunologic toxicity:

- Any Grade  $\geq$  2 non-skin, drug-related adverse event, with the following exceptions:
  - Grade 2 drug-related fatigue or laboratory abnormalities do not require a treatment delay.
- Any Grade 3 skin, drug-related adverse event
- Any Grade 3 drug-related laboratory abnormality, with the following exceptions for lymphopenia, leucopenia, AST, ALT, or total bilirubin:
  - Grade 3 lymphopenia or leucopenia does not require dose delay.
  - If a subject has baseline AST, ALT, or total bilirubin within the Grade 1 toxicity range, delay dosing for drug-related Grade  $\geq$  3 toxicity.
- Any adverse event, laboratory abnormality, or intercurrent illness which, in the judgment of the investigator, warrants delaying the dose of study medication.

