### 5.2.1 Criteria to Resume Treatment with Nivolumab

Subjects may resume treatment with nivolumab when the drug-related AE(s) resolve(s) to Grade  $\leq$  or baseline, with the following exceptions:

- Subjects may resume treatment in the presence of Grade 2 fatigue
- Subjects who have not experienced a Grade 3 drug-related skin AE may resume treatment in the presence of Grade 2 skin toxicity.
- Subjects with baseline AST/ALT or total bilirubin in the Grade 1 toxicity range who require dose delays for reasons other than a 2-grade shift in AST/ALT or total bilirubin may resume treatment in the presence of Grade 2 AST/ALT OR total bilirubin.
- Subjects with combined Grade 2 AST/ALT AND total bilirubin values meeting discontinuation parameters (section 4.4) should have treatment permanently discontinued.
- Drug-related pulmonary toxicity, diarrhea, or colitis must have resolved to Baseline before treatment is resumed. Drug-related endocrinopathies adequately controlled with only physiologic hormone replacement may resume treatment
- If treatment is delayed  $>$  6 weeks, the subject must be permanently discontinued from study therapy, except as specified in section 4.4.

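### Section 5.2's announced liver-test exception for nivolumab delay has no effect, and a line for patients with normal baseline values appears to have been left out

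*Combined protocol and SAP*

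**What the plan says.** Section 5.2 opens as a closed list: "Nivolumab administration should be only delayed for the following immunologic toxicity". Four bullets follow.

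- Bullet 1 delays for non-skin drug-related events of Grade 2 or higher, but "Grade 2 drug-related fatigue or laboratory abnormalities do not require a treatment delay".
- Bullet 2 covers Grade 3 skin events.
- Bullet 3 delays for Grade 3 drug-related laboratory abnormalities, "with the following exceptions for lymphopenia, leucopenia, AST, ALT, or total bilirubin". Two lines sit under it. One releases Grade 3 lymphopenia and leucopenia from delay. The other is the only liver line: "If a subject has baseline AST, ALT, or total bilirubin within the Grade 1 toxicity range, delay dosing for drug-related Grade" 3 or higher.
- Bullet 4 admits any event or laboratory abnormality that, "in the judgment of the investigator, warrants delaying the dose of study medication".

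Section 5.2.1 sets the restart rules. One of them allows restart with Grade 2 AST/ALT or bilirubin, but only for subjects with a Grade 1 baseline "who require dose delays for reasons other than a 2-grade shift in AST/ALT or total bilirubin". If a delay exceeds 6 weeks, "the subject must be permanently discontinued from study therapy, except as specified in section 4.4".

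Section 3.1.6 requires normal total bilirubin at entry and allows AST/ALT up to 3 times the upper limit of normal.

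**The concern.** A line placed under an exceptions heading should change what the general rule would do. The lymphopenia and leucopenia line does; the liver line does not. It is conditioned on a Grade 1 baseline, yet it gives those patients the same threshold as everyone else, and no companion line says what applies to a normal baseline.

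The unaddressed group is the ordinary patient. Bilirubin must be normal at entry, so on screening values the printed bilirubin case applies to nobody. A patient who starts normal and develops an isolated drug-related Grade 2 liver value can receive the next infusion with no rule prompting a hold. The azacitidine and entinostat table in Section 5.1 does not fill the gap: it has no liver-test row, and its row for other non-hematologic events makes no change at Grade 1 or 2, apart from a footnote holding both drugs when events are noted on day 1 of a cycle. In a multi-institutional study (Section 10.7), one site may hold and another dose.

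**Working it through.** **Step 1. Apply the text by baseline and current grade** for an isolated drug-related AST, ALT or bilirubin value. The third column strikes out the liver line. The fourth asks what would follow if a 2-grade shift were the reason for delay at every baseline, which is an extension of Section 5.2.1 and not its wording.

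| Baseline → current (shift) | Section 5.2 as printed | Liver line struck out | 2-grade shift, all baselines | Proposed text |
|---|---|---|---|---|
| Normal → Grade 2 (+2) | no hold required | no hold required | hold | hold |
| Normal → Grade 3 (+3) | hold | hold | hold | hold |
| Grade 1 → Grade 2 (+1) | no hold required | no hold required | no hold required | no hold required |
| Grade 1 → Grade 3 (+2) | hold | hold | hold | hold |

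The second and third columns are identical, so the liver line has no effect at Grade 2 or 3. It also names Grade 4, but bullet 1 already holds Grade 4, because only Grade 2 laboratory values are exempt there. The exception is therefore empty.

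**Step 2. What the gap probably held.** Three features point the same way.

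1. A line conditioned on a Grade 1 baseline serves a purpose only if another baseline has another threshold. A looser one for patients who started normal would make no clinical sense, which leaves a stricter one.
2. Section 5.2.1 describes the liver reason for delay as a 2-grade shift. From Grade 1 that is 1 + 2 = Grade 3, exactly the printed line. From normal it would be 0 + 2 = Grade 2, the absent line.
3. Section 5.2.1 grants restart at Grade 2 to Grade 1 baselines only. If Grade 2 were equally acceptable from a normal baseline, there would be little reason for the limit.

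The third is the weakest. Restart rules stricter than the hold rule also arise elsewhere, for example for other laboratory tests and for Grade 1-baseline patients held at Grade 3.

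**Step 3. Size.** Planned maximum enrolment is 66 (22 per arm). Section 6.3 lists ALT, AST and bilirubin increases with nivolumab at more than 1% up to 9% each, at any grade.

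- Per test, all arms: 0.01 × 66 = 0.66 to 0.09 × 66 = 5.94 patients.
- Per test, one arm: 0.01 × 22 = 0.22 to 0.09 × 22 = 1.98.
- With an assumed 10% to 50% of these at Grade 2: 0.10 × 0.66 = 0.066 to 0.50 × 5.94 = 2.97 of 66 per test.

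The documents give no Grade 2 share, no rate for the three-drug combination and no distribution of baseline AST/ALT.

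**Step 4. Could extra holds matter to feasibility monitoring?** Section 10.5 uses a Uniform(0,1) prior, so with x of n patients not feasible the posterior is Beta(1 + x, 1 + n − x). The rule stops when P(rate > 0.5) reaches two thirds. The printed boundary values reproduce: 6/10 gives 0.726, 9/15 gives 0.773 and 11/20 gives 0.668. One case fewer gives 0.500 (5/10), 0.598 (8/15) and 0.500 (10/20), all below 0.667. A single additional non-feasible patient can therefore tip a look, but only if that arm is already one short of the boundary.

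**The case against.** The strongest reply is that Section 5.2 is a complete rule with one threshold. Grade 2 laboratory values are expressly exempt, Grade 3 values are held, and the last bullet lets the investigator hold earlier. On that view the liver line is merely redundant, and a Grade 2 hold is a preference. Nothing in the documents states Grade 2 as the threshold for a normal baseline. Chemistry is scheduled in weeks 1, 2 and 3 of cycles 1 to 6, Section 4.4 sets discontinuation limits for liver values, including concurrent elevation, and weekly telephone conferences between sites limit divergence.

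Most of this stands. A default exists, the threshold is inferred, and the safeguards are real. What it leaves unexplained is why the section announces a liver exception, conditions it on baseline, and then excepts nothing.

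A reader might go further and infer that Sections 5.2 and 5.2.1 contradict each other, giving sites two answers for the same value. The documents do not support that. The 2-grade-shift clause is written for subjects with a Grade 1 baseline, where the shift is Grade 3 and the sections agree. Section 5.1 does not rescue the stronger reading either. Its principle, "For any event which is apparent at baseline, the dose modifications will apply according to the corresponding shift in toxicity grade", concerns azacitidine and entinostat, events already present at baseline, and cases where the investigator finds it appropriate. It says nothing about a normal baseline.

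**Conclusion.** The point holds as a defect in a safety instruction: the liver exception announced in bullet 3 has no effect, and no liver line addresses a normal baseline. Its scope is isolated drug-related Grade 2 AST, ALT or bilirubin values in patients who started normal. Grade 3 values and clinical hepatic events of Grade 2 or higher are already held. Severity is minor to moderate. On the assumed Grade 2 share the expected count is below one and at most about three patients per test, and the printed bilirubin case covers 0 of 66 on screening values.

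The empty exception can be read directly from the text. The missing threshold of Grade 2 or higher is a reasoned inference, held with medium confidence. It would be wrong to conclude that normal-baseline patients have no rule, or that the primary endpoint or the simulated operating characteristics are compromised by the omission.

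**What to change.** Three changes, in one amendment:

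1. Add to Section 5.2, bullet 3: *If baseline AST, ALT or total bilirubin is within normal limits, delay dosing for drug-related Grade ≥2 toxicity of that test.* Keep the Grade 1-baseline line, which then has a purpose.
2. Make the Grade 2 laboratory exemption in bullet 1 subject to that line, for example by adding: *except AST, ALT or total bilirubin as stated below*.
3. Confirm that Section 5.2.1 states the restart grade for these patients. The number is absent from the supplied text, possibly through PDF extraction, so this is a check and not a claimed error.

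Section 4.4 needs no change. If the sponsor does intend Grade 3 for every baseline, it should say so and remove the liver tests from the announced exceptions.

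The cost is a few more nivolumab doses held at Grade 2. A patient held on 4-weekly dosing would need an added chemistry panel, because day 15 laboratory tests are not required on that schedule (Section 8, footnote 10 for Arms D to F). An occasional hold may reach the 6-week limit, subject to the Section 4.4 exceptions, or prevent completion of six cycles and so count against feasibility. A hold that resolves and still allows six cycles does not count.

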### 5.2.1 Criteria to Resume Treatment with Nivolumab

Subjects may resume treatment with nivolumab when the drug-related AE(s) resolve(s) to Grade  $\leq$  or baseline, with the following exceptions:

- Subjects may resume treatment in the presence of Grade 2 fatigue
- Subjects who have not experienced a Grade 3 drug-related skin AE may resume treatment in the presence of Grade 2 skin toxicity.
- Subjects with baseline AST/ALT or total bilirubin in the Grade 1 toxicity range who require dose delays for reasons other than a 2-grade shift in AST/ALT or total bilirubin may resume treatment in the presence of Grade 2 AST/ALT OR total bilirubin.
- Subjects with combined Grade 2 AST/ALT AND total bilirubin values meeting discontinuation parameters (section 4.4) should have treatment permanently discontinued.
- Drug-related pulmonary toxicity, diarrhea, or colitis must have resolved to Baseline before treatment is resumed. Drug-related endocrinopathies adequately controlled with only physiologic hormone replacement may resume treatment
- If treatment is delayed  $>$  6 weeks, the subject must be permanently discontinued from study therapy, except as specified in section 4.4.

## 6. ADVERSE EVENTS: LIST AND REPORTING REQUIREMENTS

Adverse event (AE) monitoring and reporting is a routine part of every clinical trial. The following list of AEs (Section 6.1) and the characteristics of an observed AE (Section 6.2) will determine whether the event requires expedited reporting in addition to routine reporting.

### 6.1 Adverse effects of azacitidine

Very common adverse effects of azacitidine ( $\geq 10\%$ ) include anemia which may require blood transfusion, febrile neutropenia, neutropenia, leukopenia, thrombocytopenia, abdominal pain (including abdominal discomfort and upper abdominal pain), constipation, diarrhea, nausea, vomiting, asthenia, chest pain, fatigue, injection site erythema, injection site pain, injection site reaction, pyrexia, nasopharyngitis, pneumonia (including bacterial, fungal and viral), weight loss, decreased appetite, hypokalemia, arthralgia, musculoskeletal pain (includes back pain, bone pain and pain in extremity), myalgia, dizziness, headache, insomnia, dyspnea, epistaxis, ecchymosis, petechiae, pruritus (includes pruritus generalized) and rash.

Common adverse effects of azacitidine ( $\geq 1\%-<10\%$ ) include bone marrow failure, pancytopenia, conjunctival hemorrhage, eye hemorrhage, dyspepsia, gastrointestinal hemorrhage (includes mouth hemorrhage), gingival bleeding, hemorrhoidal bleeding, stomatitis, catheter site hemorrhage, chills, injection site bruising, injection site discoloration, injection site hematoma, injection site hemorrhage, injection site induration, injection site inflammation, injection site nodule, injection site pruritus, injection site rash, malaise, cellulitis, diverticulitis, neutropenic sepsis, oral fungal infection, pharyngitis, respiratory tract infection (including bronchitis and upper respiratory tract infection), rhinitis, sepsis (including bacterial, fungal and viral), sinusitis, skin infection, urinary tract infection, blood creatinine increased, dehydration, muscle spasms, intracranial hemorrhage, lethargy, somnolence, syncope, anxiety, hematuria, renal failure, shortness of breath on exertion (Dyspnea exertional), laryngeal pain, pleural effusion, alopecia, erythema, skin lesion, urticarial, hematoma, hypertension and orthostatic hypertension.

Uncommon adverse effects of azacitidine ( $\geq 0.1\%-<1\%$ ) include hypersensitivity.

